A 6-month, prospective, randomized controlled trial (RCT) of CAE vs. an educational control is being conducted in 184 poorly adherent adults with BD. To enhance generalizability, CAE is delivered by social workers. Interim RCT outcomes (CAE N=24, EDU N=26) show that CAE is associated with improved adherence as measured by the Tablet Routines Questionnaire (TRQ mean change=46.0, SD=38.7) compared to an educational control (EDU) (TRQ mean change=17.3, SD=40.3, p=.017). Six-month MEMS adherence change was also greater with CAE (mean change 45.7, SD 40.6) compared to EDU (mean change 15.9 (SD 39.9), p=.015). Effect sizes for CAE in both TRQ and MEMS are approximately 0.75, comparing favorably with effect size for response to BD medications.

Combining LAI + CAE dramatically improves adherence, symptoms and functional outcomes in people with schizophrenia and schizoaffective disorder: These investigators tested a combined LAI + CAE approach (CAE-L) in 2 preliminary studies. CAE-L Study 1 (Sajatovic 2013) enrolled 30 homeless or recently homeless individuals with schizoaffective or schizophrenia. The LAI used was haloperidol decanoate. Primary outcomes were TRQ and housing status. Secondary outcomes included psychiatric symptoms and functional status. Mean sample age was 41.8 years with a high proportion of minorities and single/never married individuals. CAE-L was associated with substantial improvement in concomitant orally prescribed medication, which changed from missing 46% of prescribed medication at study enrollment to only 10% of prescribed medication at study end. Mean proportion of time in sub-optimal housing went from 56% in the 6 months prior to study enrollment to 41% in the first 3 months of the study and 14% in the last 3 months of the study. There were also significant improvements in psychiatric symptoms and functional status.

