An important limitation of the CAE-L pilots is that they excluded individuals with BD. The pilot studies combined LAI + CAE data suggested that patients with schizoaffective disorder (N=44) did just as well as those with schizophrenia (N=16) with respect to adherence, symptom and functional outcomes (Levin et al., 2017). Combining Maintena with a practical method of adherence support has potential to enhance uptake and optimize enduring adherence to medication in patients with BD.

Project Design:

Overview: 6-month, prospective, trial testing the effects of Maintena augmented with CAE in 30 poorly adherence patients with BD. After a 2-month study start-up period, patients will be enrolled over a 16 month enrollment period (months 2-18). The targeted enrollment of approximately 2 participants/month is reasonable given previous recruitment with the CAE + LAI pilots. Primary outcomes will be change from baseline in adherence as identified by the Tablet Routines Questionnaire (TRQ) and injection frequency at the 6-month time-point. We will also evaluate changes in secondary outcomes, including BD symptoms (BPRS), depressive and global psychopathology symptoms, functional status, and adherence attitudes. Additional exploratory assessments will include health resource use, adherence barriers, substance use and neurocognition. Outcome measures will be assessed at Screening, Baseline, and Weeks 4- 24 as noted in Table 2/Study Schedule of Events. Because the study design will be nearly identical to the 2 previously conducted CAE + LAI pilots, it will be possible to compare primary and secondary outcomes of this study of individuals with BD to individuals with schizophrenia/schizoaffective disorder. The study will be operationalized in 4 specific Aims:

Aim 1: Test whether combined Maintena + CAE (Maintena +) is associated with improved treatment adherence

[figure not shown]
Hypothesis 1: At 6-month follow-up, poorly adherent BD patients receiving Maintena + will have significant improvement in medication adherence as measured by the TRQ.

Hypothesis 2: At 6-month follow-up we also expect that mean LAI adherence as measured by injection frequency will meet or exceed 80%. The 80% threshold is widely viewed in the treatment adherence literature as an “acceptable” degree of adherence.

Aim 2: Test whether Maintena + is associated with reduction in BD symptoms, improved functioning and better treatment attitudes

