Hypothesis 3: Maintena + will be associated with significant reduction in symptoms, improved functioning and better treatment attitudes.

Figure 1. Targeted mechanism of action of a customized adherence enhancement approach (CAE-L) in BD

Aim 3: Compare how individuals with BD participating in a care approach that combines LAI with a brief behavioral approach that targets adherence enhancement respond on adherence, symptom and functional outcomes in comparison to individuals with schizophrenia/schizoaffective disorder. This comparison will use outcomes from the current study vs. historical data from recently conducted trials in schizophrenia/schizoaffective disorder. Corresponding effect sizes will be computed. Based on past data comparing individuals with schizophrenia vs. those with schizoaffective disorder, we expect that BD patients will do at least as well, and possibly better than individuals with primary psychotic disorders.

Aim 4: Investigate whether improved adherence behaviors will be associated with reductions in treatment adherence barriers.

We expect that improved BD knowledge, communication with clinicians, medication routines and reduction in substance use will all be associated with improved adherence. Exploratory analysis will investigate mechanistic effect of Maintena + by evaluating whether change in BD knowledge, communication with clinicians, medication routines and substance use is related to adherence change. Additional exploratory measures will evaluate health resource use, substance use/abuse and neurocognition.

Study Population:

The study will enroll 30 individuals age 18 and over with Type 1 or Type 2 BD. Patients will be recruited from inpatient, ambulatory services and from the community by a variety of methods:

1. Study staff will inform the University Hospitals of Cleveland Medical Center (UHCMC) clinical psychiatry providers about the study.
2. Study staff will also present information about the study to the staff at local Community Mental Health Clinics (CMHCs) and other organizations serving persons with mental illness. After presenting the study in these group and individual settings, the study staff will maintain regular contact with staff at these organizations to inquire about new referrals.
3. IRB-approved recruitment fliers will be posted and distributed with permission of staff at CMHCs and other organizations serving persons with mental illness.

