4. Recruitment will be done by oral request to patients coming for regularly scheduled clinic visits at UHCMC or area CMHCs. Requests for participation may be initiated by a clinic staff member, by a research associate on site, or in some cases may be initiated by patients themselves.
5. Patients with BD will be identified from the UHCMC electronic medical record and using an IRB-approved process, be invited to participate in study screening.
6. Patients may also be recruited under the MHERP/NBOC Prescreen protocol.

All individuals with BD who are referred will be considered for possible inclusion in the study. A Screening Form for each patient will be completed regardless of whether the patient is ultimately enrolled. The form will detail reasons for exclusion, allowing an estimate of sample generalizability. Patients recruited in response to an IRB-approved recruitment method may be prescreened under the IRB-approved protocol, "Prescreening and Recruitment for the Mental Health Effectiveness Research Program and Neurological and Behavioral Outcomes Center" (MHERP/NBOC Prescreen) [IRB # 03-10-09].

The study PI ([name], Professor of Psychiatry at CWRU and UHCMC) will oversee and be responsible for all aspects of the study including study regulatory matters, human subjects requirements, study implementation, study staff supervision, and data collection, analysis and reporting. Study Co-investigators will assist the study PI in study referral, clinical and safety monitoring, training and oversight of interventionists, and participant retention. The PI has successfully conducted multiple treatment adherence studies over the last decade and has an extensive track-record of robust recruitment of non-adherent patients with BD and other serious mental illnesses. Diagnosis will be confirmed with a standardized brief interview commonly utilized in clinical trials, the Mini International Neuropsychiatric Inventory (MINI). In order to facilitate a relative comparison of BD patient response to outcomes in this study vs. recently completed pilot trials, we will deliberately recruit individuals with similar study entry level symptom severity. In the proposal trial, study entry Brief Psychiatric Symptom Rating Scale (BPRS) scores will not be below 1 standard deviation of the mean BPRS in pilot work.

Inclusion Criteria:

1. Individuals age 18 and older with BD Type 1 or 2 as confirmed by the Mini International Psychiatric Inventory (MINI).

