Sample Size and Power: We propose to enroll 30 individuals with BD who receive Maintena +. Based on our prior studies (Sajatovic 2012a, Sajatovic 2012b), we conservatively assume 20% of participants will discontinue study participation during the 24 week study period and that the effect size of CAE-L will be similar to that of CAE-L in prior studies (effect size $d=.60$). Type I error level of 0.05 will be adopted for all tests.

The primary outcomes measure will be change in adherence behavior and the mean LAI injection frequency at 6-months. Adherence rates will be calculated for TRQ in the following manner: the number of days with a missed dose will be divided by the number of days in the time period and then multiplied by 100. Adherence rates will be calculated for both the week and the month prior to assessment visit and for the study period. Given a sample size of 30 subjects with 20% attrition and two-sided Type I error of 0.05, for paired t-tests we will have power of 0.80 for effect sizes of at least 0.597. For correlations, power of 0.80 is achieved for a two-sided test of correlation being zero when the magnitude of correlation is at least 0.51. Hence, there is sufficient power to detect moderate level mean differences and correlation values. For the assessment of mean injection frequency, suppose 6 prescribed injections in 6 months, with a standard deviation of 1.2 (20% of prescribed injections). Then, if a sample mean of 5.28 or higher is observed (88%), a 95% two-sided confidence interval will not contain 4.8, the 80% threshold, This would provide evidence that the percentage of injection frequency is higher than 80%. Note that adherence levels of 80% or higher are widely considered to be "acceptable" adherence in the research literature. The mean LAI injection frequency in our previous pilot work involving LAI + CAE in homeless patients with schizophrenia exceeded 90% of prescribed injections at 6-month follow-up. We thus expect to statistically establish that the mean LAI injection frequency in this bipolar sample who are not homeless is above the 80% threshold.

Data analyses will be performed using the Statistical Analysis System (SAS) (SAS Institute, Cary, NC, 2002).. For Aim 1, change in TRQ from baseline to 24 weeks will be assessed with a paired t-test or Wilcoxon signed rank test. For mean LAI injection frequency, we will construct 95% confidence intervals. Exploratory longitudinal

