models of adherence will be considered as well. We may represent adherence as a binary outcome, indicating whether or not an adherence threshold has been met (e.g., 80% adherent), particularly if adherence levels are highly skewed. Exploratory logistic regression through generalized estimating equations (GEE) or generalized linear mixed models for binary outcomes will thus be considered for assessing effects of time. Time may be modeled with a slope parameter or treated as a categorical variable. Age, race, duration of illness, and/or gender will be considered as possible covariates. In addition, we will compare corresponding TRQ and SimpleMed pillbox adherence levels. Correlation between the adherence measures will be estimated and Bland-Altman plots will be generated (Altman 1983).

Aim 2 will evaluate change from baseline to 24 weeks in TRQ, psychiatric symptoms (BPRS, MADRS, YMRS, CGI) in a similar manner as in Aim 1. For Aim 3, change in the outcome variables and other secondary measures in the proposed study vs. historical controls (the previously conducted CAE + LAI pilots) will be compared through effect sizes. In Aim 4, adherence barriers will be evaluated as well. Mean change in symptom rating scales, functional level and medication attitudes will be estimated from baseline to the various follow up periods. We will explore whether reductions in adherence barriers (e.g., BD knowledge, medication routines, communication, and substance) will be associated with changes in adherence behavior. Correlations between respective changes in barriers and adherence levels will be computed. In a similar manner, we will also examine whether improvements in adherence behaviors correlate with improvements in symptoms, functioning, and medication attitudes.

Study reporting/deliverables: Reporting on study outcomes will be focused on rapidly available and impactful findings. As the study does not require blinding, it is expected that interim results can be used for new research abstract proposals that can be submitted even while the study is ongoing. It is expected that study results will be presented at a minimum of 2-3 suitable scientific venues including (but not limited to):

- American College of Neuropsychopharmacology (ACNP)
- American Psychiatric Association (APA)
- International Society for Bipolar Disorders (ISBD)

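### Aim 3 states a between-cohort contrast in terms of diagnosis, although LAI drug and described housing also differ and severity is matched only by a lower BPRS bound at screening

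*Combined protocol and SAP*

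**What the plan says.** Aim 3 is defined in Project Design: "This comparison will use outcomes from the current study vs. historical data from recently conducted trials in schizophrenia/schizoaffective disorder". Its expectation is worded by diagnosis: "we expect that BD patients will do at least as well, and possibly better than individuals with primary psychotic disorders". The Overview rests comparability on design: "Because the study design will be nearly identical to the 2 previously conducted CAE + LAI pilots". The analysis text for Aim 3, at the end of the section on sample size and power, says only that changes in this study and in the historical controls "will be compared through effect sizes". It names no standardising SD, confidence interval, adjustment or limit on attribution.

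Study Population promises that "we will deliberately recruit individuals with similar study entry level symptom severity". It puts this into practice as a lower bound: "scores will not be below 1 standard deviation of the mean BPRS in pilot work". Inclusion criterion 3 sets that bound at a screening BPRS of 36 or more.

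On the cohorts themselves, the Background says that CAE-L Study 1 "enrolled 30 homeless or recently homeless individuals with schizoaffective or schizophrenia. The LAI used was haloperidol decanoate". CAE-L Study 2 enrolled 30 recently homeless patients and used paliperidone palmitate. In the present trial every participant receives Maintena. Sample Size and Power describes the sample as follows: "We thus expect to statistically establish that the mean LAI injection frequency in this bipolar sample who are not homeless" will be above the 80% threshold.

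**The concern.** Aim 3 is one of four specific aims, and its result is meant to say how bipolar patients respond to LAI plus CAE relative to patients with primary psychotic disorders. At least two other things change together with diagnosis. LAI drug does not overlap at all between the cohorts, so no adjustment can separate it from diagnosis. Housing differs on the protocol's own description, and the power section itself uses that difference when predicting injection adherence. Living situation is collected at baseline but has no role in Aim 3.

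The severity match is the only stated safeguard on patient mix, and a one-sided cut cannot do what is claimed for it. It sets neither the mean nor the spread. If each cohort's effect size is divided by its own baseline SD, a narrower bipolar SD makes the same raw improvement look larger. A finding that bipolar patients did no worse, or better, could then reflect drug, housing or scaling.

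**Working it through.** **Inputs.** Pilot BPRS, Background Table 1: baseline 44.1 (SD 8.3), week 25 30.8 (SD 8.3), row N = 41 of 60 patients. No pilot BPRS is shown at screening. Floor: 36 at screening (Inclusion Criteria). Completers: 30 × 0.8 = 24 (Sample Size and Power).

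**1. The plan's floor.** 44.1 − 8.3 = 35.8, which rounds to 36. The criterion reproduces.

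**2. What a floor does to a normal distribution.** Assume the unrestricted screening BPRS is normal with the pilots' mean and SD, and that the pilots had no floor.
- α = (36 − 44.1)/8.3 = −0.976, so 16.5% fall below the floor.
- λ = φ(α)/(1 − Φ(α)) = 0.2478/0.8354 = 0.297.
- Screening mean = 44.1 + 8.3 × 0.297 = 46.6.
- Proportional loss of variance k = λ(λ − α) = 0.297 × 1.273 = 0.377.
- Screening SD = 8.3 × √(1 − 0.377) = 6.55.

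**3. Carry-over to baseline.** Change is measured from baseline, not screening. With screening-to-baseline correlation r (not given in the documents), baseline SD = 8.3 × √(1 − 0.377 r²). The pilots' fall of 44.1 − 30.8 = 13.3 points equals 13.3/8.3 = 1.60 pilot baseline SDs. The same raw fall in a floored cohort gives:

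| r (assumed) | Baseline SD | Effect size | Inflation |
|---|---|---|---|
| 0.5 | 7.9 | 1.68 | 5% |
| 0.7 | 7.5 | 1.78 | 11% |
| 0.9 | 6.9 | 1.92 | 20% |

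**4. If the SD of change is used instead.** Let c be the baseline-to-week-24 correlation. Assume equal SDs at both times and a screening-to-week-24 correlation of r × c. The variance of change, in units of 8.3², falls from 2(1 − c) to 2(1 − c) − 0.377 r²(1 − c)².
- r = 0.8, c = 0.3: 1.400 falls to 1.282, and √(1.400/1.282) = 1.045, an inflation of 4.5%.
- r = 0.6, c = 0.7: 0.600 falls to 0.588, and √(0.600/0.588) = 1.010, an inflation of 1.0%.

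So the range is about 1-5% for r of 0.6-0.8 and c of 0.3-0.7, all assumed.

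**5. Mean relative to the pilots.** The documents give no bipolar BPRS distribution. For assumed unrestricted means of 36, 40, 44.1 and 48 (SD 8.3), the floored screening mean is 42.6, 44.3, 46.6 and 49.3, and the SD is 5.0, 5.8, 6.55 and 7.2. The mean can land below, at or above 44.1. The SD is below 8.3 in each case.

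**6. Precision.** For 24 completers against 41 pilot patients, the approximate 95% half-width of a standardised between-cohort difference is 1.96 × √(1/24 + 1/41) = 0.50 SD.

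**The case against.** The case for leaving the plan alone has several good parts.

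- **Aim 3 is descriptive.** It has no numbered hypothesis, test or margin, and Study Population calls it a relative comparison. The wording is an expectation, not a conclusion. Neither the primary outcomes nor Aims 1, 2 and 4 depend on it. This stands, and it limits the consequence. It does not supply the missing limit on attribution.
- **The comparability claim concerns design, and the differences are disclosed.** This is true. But the disclosures sit in the Background and the power section, and nothing carries them into Aim 3.
- **The distortion is conditional and modest.** The power statement is for paired t-tests, which points to the SD of change, where the inflation is about 1-5%. Even the baseline-SD figures (1.60 rising to 1.68-1.92) lie within the 0.50 half-width. This stands. The plan should still name the SD, because the answer depends on it.
- **The floor acts on BPRS only.** No distortion of TRQ, injection frequency, CGI or SOFAS effect sizes has been shown.

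Three stronger readings are tempting, and the documents do not support them. A reader might take the inflation as 27% (13.3/6.55 = 2.03 against 1.60), but that needs the floor to act at baseline, and it is a screening criterion. A reader might infer that the floor makes the bipolar cohort more severe than the pilots; step 5 shows that the direction is unknown. A reader might call housing completely confounded with diagnosis, but no eligibility criterion concerns housing and the description appears only in the power section. Complete separation holds for LAI drug alone.

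**Conclusion.** The point holds as a worthwhile, low-cost improvement to a secondary aim. The attribution problem needs no distributional assumption. The cohorts differ in diagnosis, entirely in LAI drug, and in housing as described, so the comparison cannot show that a difference or a similarity is due to diagnosis. The contrast is also not simply bipolar disorder against schizophrenia, since 44 of the 60 pilot patients had schizoaffective disorder.

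The scaling problem is smaller and conditional. The BPRS effect size is inflated by about 5-20% if each cohort's own baseline SD is used, and by about 1-5% if the SD of change is used. Both ranges assume a normal, pilot-like distribution, the stated correlations and no BPRS floor in the pilots. The documents summarise the pilots without listing their eligibility criteria, so a shared floor cannot be excluded and would reduce the asymmetry. Narrowing of the SD is the more robust effect; no claim about a shift in mean relative to the pilots is warranted.

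**What to change.** 1. In the Aim 3 analysis text, compare the cohorts on raw mean change with 95% confidence intervals, adjusted for baseline if patient-level pilot data are available. Standardise any effect size in both cohorts by one common SD, named in advance.
2. In Aim 3 and in its analysis text, state that the cohorts differ in diagnosis, LAI drug and housing, and that neither a difference nor a similarity will be attributed to diagnosis.
3. Qualify the Overview's statement on closeness of design, and the Study Population statement on similar severity, to match. The latter should say that only a lower bound at screening is applied.

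Do not restrict the pilot data to BPRS of 36 or more as a remedy. Table 1 reports no pilot screening BPRS, so the filter would have to use baseline values. That would cut the pilot baseline SD directly to 6.55, while the bipolar baseline SD is cut only indirectly, to 7.7 or 7.2 at r = 0.6 or 0.8. Pilot effect sizes on baseline SD would then be 10-18% larger for the same raw change (7.23/6.55 = 1.10; 7.72/6.55 = 1.18), a bias in the other direction.

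Cost: wording and a modest change of analysis. Recruitment, treatment and sample size are unaffected. The downside is a narrower Aim 3 claim.

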2. Known to have medication treatment adherence problems as identified by the Treatment Routines Questionnaire (TRQ, 20% or more missed medications in past week or past month)
3. Screening BPRS score of ≥ 36
4. Ability to be rated on psychiatric rating scales.
5. Willingness to take LAI
6. Currently in treatment or scheduled to receive treatment at a Community Mental Health Clinic (CMHC) or other clinical setting able to provide mental health care during and after study participation
7. Able to provide written, informed consent to study participation.

Exclusion Criteria:

1. Individuals on LAI immediately prior to study enrollment.
2. Individuals with known intolerance or resistance to either oral aripiprazole or LAI formulation of aripiprazole
3. Prior or current treatment with clozapine
4. Medical condition or illness, which in the opinion of the research psychiatrist, would interfere with the patient's ability to participate in the trial
5. Physical dependence on substances (alcohol or illicit drugs) likely to lead to withdrawal reaction during the course of the study in the clinical opinion of the treated research psychiatrist
6. Immediate risk of harm to self or others
7. Female who is currently pregnant or breastfeeding

Study Medication: Medication dosing will follow recommendations in the Maintena package insert. For patients who have never received aripiprazole, there will be a brief oral tolerance testing (OTT) of up to 14 days. Individuals who tolerate OTT will then receive 400 mg of Maintena administered IM in the gluteal or deltoid location, and oral Abilify will continue for an additional 14 days, after which oral medication will be discontinued. After the initial IM injection, individuals will continue to receive injections of Maintena every month for a total of 6 months. The standard dosage of 400 mg IM will be administered in this maintenance treatment phase although clinicians may administer a lower dosage of 300 mg IM depending on clinical response.

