Safety evaluations will include baseline and Week 24/End-of-study basic laboratory evaluations (comprehensive metabolic panel, lipid profile, CBC with differential) and pregnancy testing for women. EKG will be conducted at baseline, week 4 and Week 24/End-of-study. Patient vital signs and weight will be collected at each study visit (baseline/V1, V2, V3, V4, V5, V6, V7, V8). Standardized measures of involuntary movements/ extrapyramidal symptoms will be assessed with the Simpson Angus Scale (SAS), the Barnes Akathisia Scale (BAS), the Abnormal Involuntary Movement Scale (AIMS) and the Extrapyramidal Symptoms Scale-Abbreviated version (ESRS-A). Finally, reported side effects will also be evaluated at each study visit using a form derived from the previous CAE-L studies.

Table 2: Measures and Study Schedule of Events

Visit	Screen	BL/ V1	V2	V3	V4	V5	V6	V7
Timing [†]	-14 d to -1d	0 W	4W	8W	12W	16W	20W	24W
Informed consent	X							
Inclusion/Exclusion	X							
Adherence Behavior: TRQ LAI Injection Frequency*	X	X	X	X	X	X	X	X
Non-psychotropic drug TRQ	X				X			X
MINI	X							
CAE module allocation and assessment of Adherence barriers	X							X
Physician Exam and interview	X							X
Demographics, medical burden	X							
Laboratory testing	X				X			X
EKG	X		X					X
Adherence Attitudes: DAI, AMSQ		X			X			X
Symptoms: BPRS, YMRS, MADRS, CGI	X†	X			X			X
Functioning: SOFAS, GAF		X						X
Health resource use		X						X
Alcohol/Substance Use: AUDIT, DAST-10		X			X			X
Trails A & B, Animal Fluency	X							X
Weight and vitals		X	X	X	X	X	X	X
Reported Side Effects		X	X	X	X	X	X	X
Extrapyramidal symptoms: AIMS**, SAS, BAS, ESRS-A	X	X	X	X	X	X	X	X
Patient Satisfaction					X			X
Research Clinician assessment		X	X	X	X	X	X	X
CAE sessions		X	X	X	X	X	X	X
Oral aripiprazole Dispensing***	X	X						
LAI Injection		X	X	X	X	X	X	X

[†]Timing of visits is approximate.

* LAI Injection frequency will be calculated at weeks 12 & 24.

** AIMS will only be administered at BL and W24/Term

*** Dispensing of oral medication is patient specific and may include a 14-day oral tolerability test prior to first LAI injection, or dispensing of anti-side effect medications.

† BRPS will be the only symptom evaluated at screen

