Laboratory testing includes: Comprehensive metabolic panel, CBC with differential, Thyroid function. Pre-menopausal females will require serum pregnancy testing. Women of childbearing potential must be using medically accepted methods of birth control. Week 12 lab testing will only include serum pregnancy testing for pre-menopausal females. Pregnancy testing may also be done at any time point if a woman feels she may be pregnant.

Serious Adverse Event Reporting

1. Serious adverse events (SAEs) and other safety information will be collected and reported to the relevant government authority in accordance with the current Code of Federal Regulations
2. Safety Information is defined as, any information from any source containing information such as:
 - Adverse event or suspicion thereof
 - Lack of efficacy
 - Overdose/incorrect dosage (accidental or intentional)
 - Abuse/misuse (e.g., patients sharing medication) even without resulting adverse reaction
 - Accidental exposure (e.g., child takes parent's medication)
 - Medication error
 - Withdrawal reactions
 - Disease progression/exacerbation of existing disease
 - Drug-drug/Drug-food interaction
 - Reports of unexpected benefit
 - Exposure to drug during pregnancy, where the embryo or fetus may have been exposed to medicinal products (either through maternal exposure or transmission of a medicinal product via semen following paternal exposure).
 - Exposure to drug during lactation (including uneventful)
 - Suspected counterfeit product
 - Suspected transfer of infectious disease/agent by the medicinal product concerned.
 - Product complaint report (any deficiencies related to the identity, quality, labeling, durability, reliability, efficacy, performance of a medicinal product, suspected counterfeit product)
 - Pediatric use (if not an approved use)
 - Occupational exposure
 - Off-label use (if not part of the study design)
3. SAEs and safety information will be collected from first use of an Otsuka product until 28 days after discontinuation.

Data Management & Analyses: Study data will be collected and managed using REDCap(Harris 2009), a secure, web-based application designed to support data capture for research studies.

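### Patients who take the oral tolerance test have no scheduled weight, vital-sign or AIMS value from before their first dose of study aripiprazole

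*Combined protocol and SAP*

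**What the plan says.** Study Medication sets the order of treatment. "For patients who have never received aripiprazole, there will be a brief oral tolerance testing (OTT) of up to 14 days". Then: "Individuals who tolerate OTT will then receive 400 mg of Maintena administered IM".

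Table 2 puts Screen at days -14 to -1. It marks oral aripiprazole dispensing at Screen and BL/V1, and the first injection at BL/V1. The footnote on dispensing says that it "may include a 14-day oral tolerability test prior to first LAI injection".

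On the measurements, Safety Evaluations states: "Patient vital signs and weight will be collected at each study visit (baseline/V1, V2, V3, V4, V5, V6, V7, V8". In Table 2 the weight and vitals row is blank at Screen and marked from BL/V1 to V7. The extrapyramidal row, which AIMS shares with SAS, BAS and ESRS-A, is marked at Screen, but a footnote takes AIMS out of that mark: "AIMS will only be administered at BL and W24/Term". Laboratory tests and EKG are marked at Screen.

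On events, Serious Adverse Event Reporting states: "SAEs and safety information will be collected from first use of an Otsuka product until 28 days after discontinuation".

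**The concern.** For a patient who takes the tolerance test, the visit labelled baseline is already on study drug. A change in weight, blood pressure, pulse or involuntary movements during the test becomes part of the first value recorded, and no later measurement can separate it out.

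The loss is clearest in a patient who stops during the test. That patient does not go on to the V1 injection. Even if the patient is seen at an end-of-study visit, there is no scheduled earlier value to compare with. Tolerability data matter most in this group, and a pre-drug value cannot be recovered afterwards.

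The schedule is also uneven. In a test patient, change in laboratory values to week 24 would run from before study drug, while change in weight over the same trial would run from a value taken on it.

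**Working it through.** The point rests on visit order, so the check sets the schedule entries side by side. The plan gives no figure of its own to reproduce here.

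**Step 1: where the test falls.** Oral dispensing is first marked at Screen. The test lasts up to 14 days and comes before the first injection, and the first injection is at V1 (week 0). The Screen window of 14 days holds the whole test. The order is therefore Screen, then oral aripiprazole, then V1.

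**Step 2: which safety measures have a value before the test.**

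| Measure | Screen | First scheduled value | Scheduled values before study drug (test patient) |
|---|---|---|---|
| Weight, vital signs | blank | BL/V1 | 0 of 7 (V1 to V7) |
| AIMS | excluded by footnote | BL/V1 | 0 of 2 (BL, week 24) |
| SAS, BAS, ESRS-A | marked | Screen | 1 |
| Laboratory tests, EKG | marked | Screen | 1 each |

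This takes Screen assessments as done before the first oral dose, which the order of events implies but the plan does not state.

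**Step 3: whether the text could mean otherwise.** The visit list in Safety Evaluations runs to V8, while Table 2 ends at V7. Table 2 has eight visits only if Screen is counted (1 + 7 = 8). The same section calls the first laboratory tests and EKG baseline measurements, although Table 2 puts them at Screen. So one could suppose that the text's first visit is Screen. Two things speak against this: the blank Screen cell in the weight and vitals row, and the Table 2 column heading, which ties BL and V1 to week 0.

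**Step 4: how many patients.** Only patients new to aripiprazole take the test, and the documents do not give their share of the 30. By assumed share:

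- 0%: 0 × 30 = 0 patients
- 25%: 0.25 × 30 = 7.5, so 7 or 8
- 50%: 0.50 × 30 = 15
- 100%: 1.00 × 30 = 30

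**Step 5: after the change.** With the three measures added at Screen, a test patient has 1 of 8 weight and vital-sign values and 1 of 3 AIMS values before study drug. Tolerance-test exposure before the first value falls from up to 14 days to 0.

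**The case against.** **No planned analysis is harmed.** The analysis section describes no change-from-baseline analysis of weight, vital signs or AIMS, and safety is not among the aims or the listed outcomes. This stands, and it keeps the point small. That V1 would serve as the safety reference is an inference from its label and from the lack of any earlier value.

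**A reader might infer that later safety changes will be understated.** The documents do not support that. It holds only if the change during the test runs the same way as the later change. If the two run in opposite directions, change from V1 overstates the net change. Neither direction nor size is given.

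**A reader might also measure the problem by time on drug.** With a 14-day test, 14/(14 + 28) = 33% of days on aripiprazole precede V1 when counted to V2, and 14/(14 + 168) = 8% when counted to V7. These are shares of calendar time. They would stand for bias only if change built up evenly, which nothing in the documents shows.

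**Part of the gap may already be covered.** A physician examination is scheduled at Screen and might record weight or vital signs, but the plan does not say so, and the footnote rules out AIMS there. SAS, BAS and ESRS-A cover extrapyramidal symptoms at Screen. Adverse events are collected from first product use, which, read to include the oral tablets, takes in the test. All this narrows the gap, but an event report does not replace a measured pre-drug value.

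**A reader might extend the point to efficacy,** because YMRS, MADRS and CGI also start at V1: "BRPS will be the only symptom evaluated at screen". That does not follow. V1 precedes the first injection and the first CAE session, so it is a legitimate efficacy baseline. It also fits the planned comparison with earlier work: "Because the study design will be nearly identical to the 2 previously conducted CAE + LAI pilots". Adding these ratings at Screen would be a preference and is not recommended.

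**Conclusion.** The point holds as a flaw in the safety schedule. Following Table 2 exactly, a patient who takes the oral tolerance test has no weight, vital-sign or AIMS value scheduled before study aripiprazole, and one who stops during the test cannot have a change calculated from scheduled data.

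It rests on reading Table 2 as it stands, with BL meaning the BL/V1 column, and on the Screen examination not recording these measures as a matter of routine. It concerns between 0 and 30 patients. No direction or size of bias is claimed. The TRQ and injection-frequency outcomes and the secondary outcomes are untouched. It is an optional improvement, worth making because it costs little and the missing value cannot be obtained later.

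**What to change.** - Mark weight, vital signs and AIMS at Screen in Table 2 for all patients, to be done before any oral aripiprazole is dispensed. Measuring everyone gives one reference visit for the whole sample.
- Amend the AIMS footnote to include Screen. Correct the visit list in Safety Evaluations so that it includes Screen and ends where Table 2 ends.
- Name the Screen value as the reference for changes in these three measures. Keep V1 as the efficacy baseline.
- If a patient stops during the test and is seen at an end-of-study visit, repeat the three measures then.
- Report how many patients took the test and how many stopped during it.

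The cost is a few extra minutes at an existing visit for each patient screened, including some who will not go on to treatment. No visit is added, and sample size and power do not change. One limit remains: the exclusion criteria do not bar current oral aripiprazole, so for some patients outside the test group even a Screen value may be on drug. Recording current aripiprazole use at Screen would show which patients these are.
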